5.4 Efficacy Assessments

Assessment of extracranial disease (by CT scan or other approved modalities and intracranial disease (by MRI scan) will be performed per the schedule in [Table 5.1-1](#) to [Table 5.1-4](#). Investigators may obtain more frequent follow-up MRI scans as medically indicated.

Baseline assessments should be performed within 28 days prior to first dose of study drug utilizing CT or MRI for systemic lesions and within 14 days for brain lesions (MRI only). In addition to chest, abdomen, pelvis, and brain, all known sites of disease should be assessed at baseline. Subsequent assessments should include chest, abdomen, pelvis, brain, and all known sites of disease and should use the same imaging method as was used at baseline. Subjects will be evaluated for tumor response beginning at 6 weeks (± 7 days) from the first dose of study drugs for the first 12 months and every 12 weeks (± 7 days) thereafter, until disease progression is documented or treatment is discontinued (whichever occurs later). Tumor assessments for ongoing

study treatment decisions will be completed by the investigator using RECIST (Response Evaluation Criteria in Solid Tumors) 1.1 criteria for all systemic lesions and modified RECIST 1.1 for brain lesions ([Appendix 3](#)).

Radiographic images will be collected and sent to a centralized imaging core laboratory for storage and potential future central reading.

All radiologic imaging from this study will be assessed at the study site by the Investigator. Sites will be trained in image acquisition parameters, image analyses, and submission process, prior to scanning the first study subject. These guidelines will be outlined in a separate CA209204 Site Imaging Manual.

For extracranial disease assessment, contrast-enhanced computed tomography (CT) scans acquired on dedicated CT equipment is preferred for this study. CT with contrast of the chest, abdomen and pelvis and other areas of disease are to be performed for tumor assessments per [Table 5.1-1](#) to [Table 5.1-4](#). Should a subject have a contraindication for CT IV contrast, a non-contrast CT of the chest and a contrast enhanced MRI of the abdomen and pelvis may be obtained. MRI's should be acquired with slice thickness of ≤ 5 mm with no gap (contiguous).

Use of CT component of a PET/CT scanner: Combined modality scanning such as with FDG-PET/CT is increasingly used in clinical care, and is a modality/technology that is in rapid evolution; therefore, the recommendations outlined here may change rather quickly with time. At present, low dose or attenuation correction CT portions of a combined FDG-PET/CT are of limited use in anatomically based efficacy assessments and it is therefore suggested that they should not be substituted for dedicated diagnostic contrast enhanced CT scans for anatomically based RECIST measurements. However, if a site can document that the CT performed as part of a FDG-PET/CT is of identical diagnostic quality to a diagnostic CT (with IV and oral contrast) then the CT portion of the FDG-PET/CT can be used for RECIST 1.1 measurements. Note, however, that the FDG-PET portion of the CT introduces additional data which may bias an investigator if it is not routinely or serially performed.

MRI scans: Bi-dimensional and three-dimensional contrast enhanced MRI of the brain will be acquired per the CA209204 Imaging Manual requirements. Every attempt should be made to image each subject using an identical acquisition protocol on the same scanner for all imaging time points. Cases of suspected radiologic disease progression will be confirmed by an MRI performed approximately 4 weeks after the initial radiological assessment of progression.

5.4.1 Computed Tomography Imaging (CT)

Baseline CT assessments should be performed within 28 days prior to enrollment. In addition to chest, abdomen, pelvis, all known sites of disease should be assessed at baseline.

Subsequent CT assessments should occur at +/- 7 days per scheduled visits and should include chest, abdomen, and pelvis, and all known sites of disease. The same imaging method used at baseline should be used for all CT assessments. Subjects will be evaluated for tumor response every 6 weeks for Year 1 and every 12 weeks thereafter until progression or discontinuation, whichever is later.

5.4.2 Brain Magnetic Resonance Imaging (MRI)

All subjects will receive efficacy assessments with brain MRI at time points specified in [Table 5.1-1](#) to [Table 5.1-4](#). Baseline brain MRI should be performed with 14 days prior to enrollment.

All MRIs should occur at ± 7 days per scheduled visits. Investigators may obtain more frequent follow-up MRI scans as medically indicated.

5.4.3 Confirmation of Scans

Verification of Response: Confirmation of intracranial response will be confirmed by an MRI performed approximately 4 weeks after the initial radiological assessment. If repeat scans confirm overall response (OR), then response should be declared using the date of the initial scan. If repeat scans do not confirm OR, then the subject is considered not to have had an OR.

Verification of Progression: Progression of disease should be verified in cases where progression is equivocal and will be confirmed by an MRI performed approximately 4 weeks after the initial radiological assessment of progression. If repeat scans confirm PD, then progression should be declared using the date of the initial scan. If repeat scans do not confirm PD, then the subject is considered not to have progressive disease.

5.4.4 Algorithms for Response Assessments

5.4.4.1 Primary Efficacy Assessment

The primary endpoint of the study is intracranial CBR ≥ 6 months in subjects with malignant melanoma with intracranial metastases treated with nivolumab combined with ipilimumab therapy. Tumor response will be based on Investigator assessment using modified RECIST 1.1.

5.4.4.2 Secondary Efficacy Assessments

The secondary efficacy endpoints include extracranial CBR ≥ 6 months using RECIST 1.1 and will be based on Investigator assessment.

Additional secondary endpoints are specified in [Section 8.4.2](#).

[REDACTED]

5.8 Results of Central Assessments

All radiologic imaging from this study will be transmitted to a centralized imaging core laboratory for storage and analysis. Sites will be informed of quality issues or the need for repeat scanning via queries from the core lab. The details of the independent review conducted by the Independent Radiologic Review Committee (IRRC) are outlined in a separate CA209204 Imaging Review Charter.

All efficacy objectives will be evaluated by Investigator assessment based on local radiologic tumor measurements using a modified RECIST 1.1 for intracranial and RESCIST 1.1 for extracranial ([Appendix 3](#)).

6 ADVERSE EVENTS

An *Adverse Event (AE)* is defined as any new untoward medical occurrence or worsening of a preexisting medical condition in a clinical investigation subject administered study drug and that does not necessarily have a causal relationship with this treatment. An AE can therefore be any unfavorable and unintended sign (such as an abnormal laboratory finding), symptom, or disease temporally associated with the use of study drug, whether or not considered related to the study drug.

The causal relationship to study drug is determined by a physician and should be used to assess all adverse events (AE). The causal relationship can be one of the following:

Related: There is a reasonable causal relationship between study drug administration and the AE.

Not related: There is not a reasonable causal relationship between study drug administration and the AE.

The term "reasonable causal relationship" means there is evidence to suggest a causal relationship.

Adverse events can be spontaneously reported or elicited during open-ended questioning, examination, or evaluation of a subject. (In order to prevent reporting bias, subjects should not be questioned regarding the specific occurrence of one or more AEs.)

6.1 Serious Adverse Events

A *Serious Adverse Event (SAE)* is any untoward medical occurrence that at any dose:

- results in death

- is life-threatening (defined as an event in which the subject was at risk of death at the time of the event; it does not refer to an event which hypothetically might have caused death if it were more severe)
- requires inpatient hospitalization or causes prolongation of existing hospitalization (see **NOTE** below)
- results in persistent or significant disability/incapacity
- is a congenital anomaly/birth defect
- is an important medical event (defined as a medical event(s) that may not be immediately life-threatening or result in death or hospitalization but, based upon appropriate medical and scientific judgment, may jeopardize the subject or may require intervention [eg, medical, surgical] to prevent one of the other serious outcomes listed in the definition above.) Examples of such events include, but are not limited to, intensive treatment in an emergency room or at home for allergic bronchospasm; blood dyscrasias or convulsions that do not result in hospitalization.) Potential drug induced liver injury (DILI) is also considered an important medical event. (See [Section 6.6](#) for the definition of potential DILI.)

Suspected transmission of an infectious agent (eg, pathogenic or nonpathogenic) via the study drug is an SAE.

Although pregnancy, overdose, cancer, and potential drug induced liver injury (DILI) are not always serious by regulatory definition, these events must be handled as SAEs. (See [Section 6.1.1](#) for reporting pregnancies).

NOTE:

The following hospitalizations are not considered SAEs in BMS clinical studies:

- a visit to the emergency room or other hospital department < 24 hours, that does not result in admission (unless considered an important medical or life-threatening event)
- elective surgery, planned prior to signing consent
- admissions as per protocol for a planned medical/surgical procedure
- routine health assessment requiring admission for baseline/trending of health status (eg, routine colonoscopy)
- medical/surgical admission other than to remedy ill health and planned prior to entry into the study. Appropriate documentation is required in these cases
- admission encountered for another life circumstance that carries no bearing on health status and requires no medical/surgical intervention (eg, lack of housing, economic inadequacy, caregiver respite, family circumstances, administrative reason).
- Admission for administration of anticancer therapy in the absence of any other SAEs (applies to oncology protocols)

6.1.1 Serious Adverse Event Collection and Reporting

Sections 5.6.1 and 5.6.2 in the IB represent the Reference Safety Information to determine expectedness of serious adverse events for expedited reporting. Following the subject's written consent to participate in the study, all SAEs, whether related or not related to study drug, must be collected, including those thought to be associated with protocol-specified procedures. All SAEs

must be collected that occur during the screening period and within 100 days of discontinuation of dosing.

The investigator should report any SAE that occurs after these time periods and that is believed to be related to study drug or protocol-specified procedure.

An SAE report should be completed for any event where doubt exists regarding its seriousness.

If the investigator believes that an SAE is not related to study drug, but is potentially related to the conditions of the study (such as withdrawal of previous therapy or a complication of a study procedure), the relationship should be specified in the narrative section of the SAE Report Form.

SAEs, whether related or not related to study drug, and pregnancies must be reported to BMS (or designee) within 24 hours. SAEs must be recorded on the SAE Report Form; pregnancies on a Pregnancy Surveillance Form (electronic or paper forms). The preferred method for SAE data reporting collection is through the eCRF. The paper SAE/pregnancy surveillance forms are only intended as a back-up option when the eCRF system is not functioning. In this case, the paper forms are to be transmitted via email or confirmed facsimile (fax) transmission to:

SAE Email Address: [contact]

SAE Facsimile Number: See Contact Information list.

For studies capturing SAEs through electronic data capture (EDC), electronic submission is the required method for reporting. The paper forms should be used and submitted immediately, only in the event the electronic system is unavailable for transmission. When paper forms are used, the original paper forms are to remain on site.

SAE Telephone Contact (required for SAE and pregnancy reporting): Refer to Contact Information list.

If only limited information is initially available, follow-up reports are required. (Note: Follow-up SAE reports should include the same investigator term(s) initially reported.)

If an ongoing SAE changes in its intensity or relationship to study drug or if new information becomes available, a follow-up SAE report should be sent within 24 hours to the BMS (or designee) using the same procedure used for transmitting the initial SAE report.

All SAEs should be followed to resolution or stabilization.

6.2 Nonserious Adverse Events

A *nonserious adverse event* is an AE not classified as serious.

6.2.1 Nonserious Adverse Event Collection and Reporting

The collection of nonserious AE information should begin at initiation of study drug. Nonserious AE information should also be collected from the start of a placebo lead-in period or other observational period intended to establish a baseline status for the subjects.

Nonserious AEs should be followed to resolution or stabilization, or reported as SAEs if they become serious (see [Section 6.1.1](#)). Follow-up is also required for nonserious AEs that cause

interruption or discontinuation of study drug and for those present at the end of study treatment as appropriate. All identified nonserious AEs must be recorded and described on the nonserious AE page of the CRF (paper or electronic).

Completion of supplemental CRFs may be requested for AEs and/or laboratory abnormalities that are reported/identified during the course of the study.

6.3 Laboratory Test Result Abnormalities

The following laboratory test result abnormalities should be captured on the nonserious AE CRF page or SAE Report Form (paper or electronic) as appropriate:

- Any laboratory test result that is clinically significant or meets the definition of an SAE
- Any laboratory test result abnormality that required the subject to have study drug discontinued or interrupted
- Any laboratory test result abnormality that required the subject to receive specific corrective therapy.

It is expected that wherever possible, the clinical rather than laboratory term would be used by the reporting investigator (eg, anemia versus low hemoglobin value).

6.4 Pregnancy

If, following initiation of the study drug, it is subsequently discovered that a study subject is pregnant or may have been pregnant at the time of study exposure, including during at least 5 half lives after product administration, the investigator must immediately notify the BMS Medical Monitor/designee of this event and complete and forward a Pregnancy Surveillance Form to BMS Designee within 24 hours and in accordance with SAE reporting procedures described in [Section 6.1.1](#).

In most cases, the study drug will be permanently discontinued in an appropriate manner (eg, dose tapering if necessary for subject safety).

In the rare event that the benefit of continuing study drug is thought to outweigh the risk, after consultation with BMS, the pregnant subject may continue study drug after a thorough discussion of benefits and risk with the subject

Protocol-required procedures for study discontinuation and follow-up must be performed on the subject unless contraindicated by pregnancy (eg, x-ray studies). Other appropriate pregnancy follow-up procedures should be considered if indicated.

The investigator must immediately notify the BMS (or designee) Medical Monitor of this event and complete and forward a Pregnancy Surveillance Form to BMS (or designee) within 24 hours and in accordance with SAE reporting procedures described in Section 6.1.1.

Follow-up information regarding the course of the pregnancy, including perinatal and neonatal outcome and, where applicable, offspring information must be reported on the Pregnancy Surveillance Form.

Any pregnancy that occurs in a female partner of a male study participant should be reported to BMS. Information on this pregnancy will be collected on the Pregnancy Surveillance Form.

6.5 Overdose

An overdose is defined as the accidental or intentional administration of any dose of a product that is considered both excessive and medically important. All occurrences of overdose must be reported as an SAE (see Section 6.1.1 for reporting details).

6.6 Potential Drug Induced Liver Injury (DILI)

Wherever possible, timely confirmation of initial liver-related laboratory abnormalities should occur prior to the reporting of a potential DILI event. All occurrences of potential DILIs, meeting the defined criteria, must be reported as SAEs (see Section 6.1.1 for reporting details).

Potential drug induced liver injury is defined as:

- 1) ALT or AST elevation > 3 times upper limit of normal (ULN)

AND

- 2) Total bilirubin > 2 times ULN, without initial findings of cholestasis (elevated serum alkaline phosphatase),

AND

- 3) No other immediately apparent possible causes of AT elevation and hyperbilirubinemia, including, but not limited to, viral hepatitis, pre-existing chronic or acute liver disease, or the administration of other drug(s) known to be hepatotoxic.

6.7 Other Safety Considerations

Any significant worsening noted during interim or final physical examinations, electrocardiogram, X-ray filming, any other potential safety assessment required or not required by protocol should also be recorded as a nonserious or serious AE, as appropriate, and reported accordingly.

7 DATA MONITORING COMMITTEE AND OTHER EXTERNAL COMMITTEES

A Data Monitoring Committee external to BMS will not be used in this study. A Steering Committee will be created and composed of a core group of study investigators who are experts in treating patients with melanoma brain metastases with sponsor physicians/ study staff. The steering committee will be informed if a safety signal emerges and will be informed of the results of the interim analyses. After review of the available safety and tolerability data from the interim analysis, the Steering Committee will recommend continuation, modification or termination of the study.

8 STATISTICAL CONSIDERATIONS

8.1 Sample Size Determination

The total sample size for the treatment of nivolumab combined with ipilimumab is 110 subjects. All patients will contribute to the primary efficacy assessment.

Cohort A will enroll asymptomatic subjects (n ~ 90), and Cohort B will enroll symptomatic subjects (defined in Section 3.3.1).

Table 8.1-1 presents the clinical benefit rates (CBRs) that would have to be observed to yield clinically meaningful results with respect to the lower bounds of the Clopper-Pearson exact two sided 90% and 95% CI. The planned sample size ensures that the maximum width of the exact 90% CI for any given CBR estimate does not exceed 18% and the maximum width of the exact 95% CI for any given CBR estimate does not exceed 20%.

Table 8.1-1: CA209204: Clinical Benefit Rates – two sided 90% confidence interval (Clopper-Pearson)

Nivolumab + Ipilimumab (n=110)				
	Clinically meaningful CBR	Observed CBR	Clopper-Pearson exact two-side 90% CI	Clopper-Pearson exact two-side 95% CI
Brain (intracranial)	40%	53/110 (48.2%)	(40.0%, 56.4%)	(38.5%, 57.9%)
		57/110 (51.8%)	(43.6%, 60.0%)	(42.1%, 61.5%)
Systemic (extracranial)/ Global (intracranial +extracranial)	50%	65/110 (59.1%)	(50.8%, 67.0%)	(49.3%, 68.4%)

CBR = Clinical Benefit Rate

If the observed intracranial CBR rate is 51.8%, the sample size of 110 will achieve 80.4% power to detect a difference of 11.8% (51.8% versus 40% historical intracranial CBR rate) with a type I error rate of 0.10 for the two-sided binomial test.

8.2 Populations for Analysis

- All Enrolled Subjects: All subjects who signed an informed consent form and were registered into the IVRS
- All Treated Subjects: All subjects who received at least one dose of any study medication.

8.3 Endpoint Definitions

8.3.1 Tumor Assessment Endpoints

8.3.1.1 Best Overall Response (BOR) per Subject

The best overall response is determined once all the data for the subject is known. It is defined as the best response designation, as determined by the investigator, recorded between the date of first dose of study drug and the date of objectively documented progression or the date of subsequent therapy, whichever occurs first. For subjects without documented progression or subsequent therapy, all available response designations will contribute to the BOR assessment.

In this study, BOR is specified for the intracranial, extracranial, and global compartments based on the (1) modified RECIST 1.1 criteria (intracranial), (2) RECIST 1.1 criteria (extracranial), (3) combination of modified RECIST 1.1 criteria and RECIST 1.1 criteria (global). Image assessment criteria (modified RECIST 1.1 and RECIST 1.1) are presented in [Appendix 3](#).

For the assessment of BOR, all available assessments per subject are considered.

The best overall response for each patient is determined from the sequence of overall (lesion) responses according to the following rules, listed in order of priority:

- CR = At least two determinations of CR at least 4 weeks apart before progression.
- PR = At least two determinations of PR or better at least 4 weeks apart before progression (and not qualifying for a CR).
- SD = At least one SD assessment \geq 6 months after start of treatment.
- PD = At least two determinations of PD at least 4 weeks apart after start of treatment (and not qualifying for CR, PR or SD).

The BOR for each patient will also be determined by the IRRC as specified within the CA209204 Imaging Review Charter.

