8.4 Endpoints

8.4.1 Primary Endpoint

Intracranial clinical benefit rate (CBR) defined as the proportion of patients, whose best overall response according to modified RECIST1.1, is either complete response (CR), a partial response (PR) or stable disease (SD).

The primary endpoint is intracranial CBR. It is defined as the proportion of all treated subjects whose best overall response is either a CR or PR or whose best overall response was SD with duration of \geq 6 months, as determined by modified RECIST 1.1 criteria for index intracranial lesions based on investigator review.

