4 ENDPOINTS

4.1 Primary Endpoints

The primary endpoint is intracranial CBR. It is defined as the proportion of all treated subjects whose best overall response (BOR) is either a CR or PR or whose BOR was SD with duration of ≥ 6 months, as determined by modified RECIST 1.1 criteria for index intracranial lesions based on investigator review.

The BOR is defined as the best response designation recorded between the date of first study dosing date and the date of progression, or the date of subsequent anticancer therapy (including tumor-directed radiotherapy and tumor-directed surgery), whichever occurs first. In this study, BOR is specified for the intracranial, extracranial, and global compartments based on the (1) modified RECIST 1.1 criteria (intracranial), (2) RECIST 1.1 criteria (extracranial), (3) combination of modified RECIST 1.1 criteria and RECIST 1.1 criteria (global). Best response determination in trials where confirmation of complete or partial response is required: Complete or partial responses may be claimed only if the criteria for each are met at a subsequent time point as specified in protocol Appendix 3. There is no confirmation requirement for progressive disease (PD). The BOR for each patient as determined by the BICR is determined from a predefined set of rules specified within the Image Review Charter.

To ensure the accuracy of primary endpoints, analyses will be based on two sets of BOR: BOR as reported in the CRF and BOR with adjustment. BOR as reported in the CRF uses information entered in the CRF directly by investigators without adjustment. Results based on BOR with adjustments will serve as primary analysis. This decision was made after the interim database lock on 09 August 2020.

BOR with adjustment uses information entered in the CRF with the following adjustments:

- If BOR is NE, and the radiographic progression date is non-missing and prior to subsequent anti-cancer therapy start date, or subsequent anti-cancer therapy start date is missing, change BOR to PD.
- If BOR is SD, and the radiographic progression date is non-missing and duration of SD is less than 6 months and radiographic progression date is prior to subsequent anti-cancer therapy start date, or subsequent anti-cancer therapy start date is missing, change BOR to PD.
- If BOR is PR or CR, and there is preceding (confirmed or unconfirmed) PD and

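### Protocol 8.3.1.1 credits SD only when a scan at or after 6 months is itself called SD, which conflicts with the duration-based definition in protocol 8.4.1 and SAP 4.1 and can leave a late unconfirmed response uncounted

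*Protocol*

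**What the plan says.** Protocol 8.3.1.1 gives an ordered list of BOR rules for the intracranial, extracranial and global compartments:

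- Complete response: "CR = At least two determinations of CR at least 4 weeks apart before progression".
- Partial response: "PR = At least two determinations of PR or better at least 4 weeks apart before progression", and not qualifying for CR.
- Stable disease: "SD = At least one SD assessment" at or after 6 months from the start of treatment.
- Progressive disease: two PD determinations at least 4 weeks apart, in a subject who qualifies for none of the above.

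Protocol 8.4.1 defines the primary endpoint, intracranial CBR, by duration rather than by the label on one scan. It counts treated subjects "whose best overall response is either a CR or PR or whose best overall response was SD with duration of" at least 6 months. SAP 4.1 does the same: "whose best overall response (BOR) is either a CR or PR or whose BOR was SD with duration of" at least 6 months. The SAP does not repeat the four-line list. Its primary analysis starts from the BOR that the investigator enters in the CRF and applies a short set of adjustments.

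On unconfirmed responses, protocol 5.4.3 states: "If repeat scans do not confirm OR, then the subject is considered not to have had an OR". SAP 4.1 states: "Complete or partial responses may be claimed only if the criteria for each are met at a subsequent time point", and refers to protocol Appendix 3. Neither statement says which category the subject then falls into.

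**The concern.** The PR line is inclusive and the SD line is not. Under the literal SD line, a better reading on the one scan that matters can cost the subject the endpoint: SD on that scan is clinical benefit, while a single PR or CR on it is neither a response nor SD. An endpoint meant to capture disease control for at least 6 months should not rank those two records that way round.

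The protocol also contains two tests for the same thing, a label on a scan past 6 months (8.3.1.1) and a duration of SD (8.4.1, repeated in SAP 4.1). They can disagree on the same subject. BOR is assessed by the investigator in an open-label, single-arm trial, so two sites could code the same scans differently in the primary endpoint. Extracranial and global CBR depend on the same list.

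**Working it through.** **Inputs.** n = 110, reference rate 40%, assumed rate 51.8%, two-sided type I error 0.10, stated power 80.4% (protocol 8.1, SAP 5). Scans every 6 weeks ± 7 days in year 1 (protocol Tables 5.1-2 and 5.1-3). One month = 30.4375 days (SAP 8.1.2). Confirmatory MRI at about 4 weeks (protocol 5.4.3).

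**The plan's own figures.** The smallest r with P(X ≥ r | 110, 0.40) ≤ 0.05 is 53, with tail probability 0.0499. Exact power is P(X ≥ 53 | 110, 0.518) = 80.4%, as stated. The Clopper-Pearson 90% interval for 53/110 is 40.00% to 56.44%, which agrees with protocol Table 8.1-1.

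**Which scan can qualify.** Six months = 6 × 30.4375 = 182.6 days. The Week 24 window is Days 161 to 175, which is too early. The Week 30 window is Days 203 to 217. Week 30 is therefore the first scheduled scan that can meet the SD rule.

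**Literal application of 8.3.1.1.** All records have SD at Weeks 6, 12, 18 and 24.

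| Week 30 | Afterwards | CR or PR? | SD? | Clinical benefit |
|---|---|---|---|---|
| SD | PD at Week 36 | No | Yes | Yes |
| PR or CR | PD at Week 36 | No, one determination | No, no SD-labelled scan past 6 months | No |
| PR or CR | Death, subsequent therapy, or no further evaluable scan | No | No | No |
| PR or CR | SD on repeat MRI near Week 34 | No | Yes | Yes |
| PR or CR | PR or better on a repeat at least 4 weeks later | Yes | – | Yes |

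In the second row the subject is PD only if a second PD scan follows at least 4 weeks later. With one PD scan or none, no line of the list applies.

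**The same record under SAP 4.1.** Take PR at Week 30 and PD at Week 36, with the investigator entering SD. The SAP changes SD to PD only if progression is recorded and SD lasted less than 6 months. SD duration is not defined in the supplied text, and the answer depends on where it ends:

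- last scan called SD, Week 24: 24 × 7 = 168 days, under 182.6, so changed to PD and not benefit;
- Week 30 scan: 30 × 7 = 210 days, benefit;
- progression at Week 36: 36 × 7 = 252 days, benefit.

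None of the listed adjustments turns an unconfirmed CR or PR into SD.

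**Size.** Each affected subject is 1/110 = 0.9 points of CBR. The frequency is not in the documents. As an assumption, let 2–5% of subjects first respond at Week 30 and let 20–40% of those be neither confirmed nor re-read as SD. Then 0.02 × 0.20 = 0.4% to 0.05 × 0.40 = 2.0% are affected, or 0.4 to 2.2 of 110, about 0 to 2 subjects.

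| Expected subjects lost | True rate as counted | Exact power, P(X ≥ 53) |
|---|---|---|
| 0 | 51.8% | 80.4% |
| 1 | 50.9% | 74.7% |
| 2 | 50.0% | 68.2% |

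At the boundary, 53/110 has a 90% lower limit of 40.00% and 52/110 has 39.12%.

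**The case against.** The strongest reply is that the governing analysis does not use the 8.3.1.1 list. SAP 4.1 takes the investigator's CRF entry. Once 5.4.3 has withdrawn the unconfirmed response, the remaining pre-progression designations are SD, so the investigator can enter SD and the subject can count. This stands. A reader might infer that these subjects certainly drop out of the primary endpoint, and the documents do not support that. What remains is that the outcome turns on an undefined duration and on each investigator's reading.

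Second, 5.4.3 calls for a repeat MRI about 4 weeks after an intracranial response, so the record needs that scan to show PD, be unevaluable or never happen. This also stands and makes the case narrow. That repeat is described only for intracranial response, so it offers less protection for extracranial CBR.

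Third, Appendix 3, cited for both the response criteria and confirmation, is not in the supplied text and may settle how an unconfirmed response is categorised. Its absence here is not a gap in the plan. The conflict between 8.3.1.1 and 8.4.1 is visible without it.

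Fourth, the schedule tables gloss 12 months as week 48. Read that way, 6 months would be Week 24, and the critical scan would move from Week 30 to Week 24. The ordering problem would remain.

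Two further inferences should be resisted. The uncounted subjects are not shown to have longer control than the counted ones: in the matched records, control lasts equally long and only the depth at one scan differs. And the fact that one subject moves the lower limit across 40% is true of any one-subject change at the boundary, so it does not show that this issue will matter.

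**Conclusion.** The point holds as an internal conflict with a narrow reach. Protocol 8.3.1.1, taken literally, gives the wrong ordering for a subject whose only evaluable scan past 6 months is a single unconfirmed PR or CR, and it disagrees with protocol 8.4.1 and SAP 4.1. Whether such a subject is lost from the SAP primary analysis depends on the CRF entry, on the undefined SD duration and possibly on Appendix 3.

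The effect is 0.9 points of CBR per subject. The range of 0 to 2 subjects, and the corresponding power of 80.4% down to 68.2%, rests wholly on assumed frequencies and on every affected subject being lost. Any bias from the rule is downward, so against the 40% reference it is conservative and cannot create a false positive. It is worth correcting because it sits in the primary endpoint definition and is cheap to repair, not because a large distortion has been shown.

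**What to change.** In protocol 8.3.1.1, replace the SD line with: *SD = at least one assessment of SD or better at least 6 months after start of treatment, before progression or subsequent therapy, and not qualifying for CR or PR.*

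In SAP 4.1, state that an unconfirmed CR or PR counts as SD both for BOR and for SD duration, and define SD duration in the same terms, including its start and end. Check both texts against Appendix 3 so that all three agree.

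The cost is one line in the protocol and a sentence or two in the SAP. No new data or scans are needed. If outcome data have already been seen when the change is made, report CBR under both readings and list the subjects whose classification differs.
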